01.24.2017

**THE CLINICAL EFFECTS OF EXERCISE PROGRAM ADDED
TO PULMONARY REHABILITATION PROGRAM IN PATIENTS
WITH CYSTIC FIBROSIS**

NCT Number: 03295201

This study was planned to be a prospective single-blinded randomized controlled study and was performed between March 2017 and October 2017. Local ethics committee approval was taken (Marmara University, Istanbul, Turkey). Informed consents were obtained from the families of children. The inclusion and exclusion criteria were determined as shown below:

Inclusion Criteria

1. Patients diagnosed with cystic fibrosis (CF)
2. Patients aged between 6-14
3. FEV1 greater than 30%

Exclusion Criteria

1. Presence of cor pulmonale
2. Spinal fracture story
3. Currently under IV medication
4. Severe gastroesophageal reflux

The patients were equally randomized into two groups according to the closed envelope system. One group planned to treat six weeks with pulmonary rehabilitation and postural exercise program (Group 1), while other group being treated with pulmonary rehabilitation program alone (Group 2). Patients were assessed for respiratory function with FEV1, pain level with Visual Analog Scale (VAS), quality of life with The Cystic Fibrosis Questionnaire-Revised Child Version (CFQR), exercise tolerance with Modified Shuttle Test (MST) and postural stability with Neurocom Balance Master® Device Limits of Stability Test (LOS). All tests were performed before treatment and six weeks, three months and six months after treatment. Cobb and Modifiye Cobb angles were measured on radiographic examinations to evaluate spinal deformities before and six months after treatment.

Treatment:

Pulmonary Rehabilitation

Active cycle of breathing techniques (ACBT) was preferred for pulmonary rehabilitation. ACBT was applied by a therapist once per a week for six weeks. A daily schedule was given for the other days of the week to ensure permanence of treatment. ACBT is a commonly used chest physiotherapy method for secretion removal from lungs. Each ACBT cycle consists a sequence of breathing control, thoracic expansion exercises and forced expiration technique. These cycles are performed consecutively until the secretion is completely discharged.

Postural exercise Program

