Thoracic vertebra mobilization, pectoral stretching, scapula and thoracic extensors strengthening and core stability exercises were applied by a therapist once per a week for six weeks. A daily schedule was given for the other days of the week to ensure permanence of treatment.

Assessment:

The Cystic Fibrosis Questionnaire-Revised (CFQR)

The Cystic Fibrosis Questionnaire-Revised is the most commonly used quality of life measurement tool in patients with CF and is found to be valid and reliable in Turkish. The child version of this test consists 35 questions about physical function, emotional function, social function, body appearance, eating disorders, treatment difficulties, respiratory and digestive symptoms. Total score is calculated between 0-100 and higher scores define better condition.

Modified Shuttle Test (MST)

The Modified Shuttle Test is an easy test that can show exercise tolerance and cardiorespiratory status in children with CF. The patient is asked to walk until feeling tired between two fixed objects with a 10-meter interval, starting at normal walking speed and increasing the speed at the beginning of each minute. Maximum distance is measured for the test.

Limits of Stability Test (LOS)

The Limits of Stability Test consists a 18x60 inch of a pressure platform which connected to a computer system. The patient is asked to stand on the platform barefoot and watch the image which can be moved by trunk movement on the computer the monitor. It is required to move the image towards to target points on monitor with commands. Reaction time, movement velocity, endpoint excursion, maximum excursion and direction control parameters are calculated during these trunk movements.

Radiographic evaluation

The Cobb angle was measured on antero-posterior scoliosis graphs by the angle between the superior end plate of the vertebra corpus where the curve begins and the end plate of the vertebra corpus which the curve ends. The Modified Cobb angle was found on lateral scoliosis graphs by the angle between the superior end plate of the T4 vertebra corpus and the inferior end plate of the T12 vertebra corpus.

Statistical analysis

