Statistical analysis of the study was calculated using the SPSS for Windows 20.0 program. Normal distribution of quantitative values was assessed by histogram, Q-Q graph and normality tests. The Mann-Whitney U test was used to compare the measurement values between the two groups, and the Friedman test was used to compare the intra-group parameters. A statistical significance level of $p < 0,05$ was accepted. The Wilcoxon test was used to compare pre-treatment and post-treatment 6th-week, 3rd-month and 6th-month values separately. Bonferroni correction was considered $p < 0,017$ statistically significant for evaluating the results. A Spearman and Pearson correlation analysis was performed to examine the relationship between the radiographic values measured by two different clinicians. The intraclass correlation coefficient for the interobserver reliability analysis was calculated for radiographic measurements.

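### The between-group tests that answer the randomised question are read at 0.05, with no primary outcome, primary visit or multiplicity rule named; the only correction stated fits the within-group comparisons

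*Combined protocol and SAP*

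**What the plan says.** All statements on testing are in the Statistical analysis section. For the group comparison: "The Mann-Whitney U test was used to compare the measurement values between the two groups". After a clause on the Friedman test within groups comes the general level: "A statistical significance level of $p < 0,05$ was accepted". The within-group follow-up is next: "The Wilcoxon test was used to compare pre-treatment and post-treatment 6th-week, 3rd-month and 6th-month values separately". The correction comes straight after that: "Bonferroni correction was considered $p < 0,017$ statistically significant for evaluating the results".

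The measures are listed in the opening study description and under Assessment. The description begins "Patients were assessed for respiratory function with FEV1, pain level with Visual Analog Scale (VAS" and goes on to quality of life (CFQR), exercise tolerance (MST) and postural stability (LOS). On timing it says "All tests were performed before treatment and six weeks, three months and six months after treatment". The radiographs have one post-treatment time point: "Cobb and Modifiye Cobb angles were measured on radiographic examinations to evaluate spinal deformities before and six months after treatment". Under Assessment, CFQR has a total score from 0 to 100 and several content areas, MST yields a distance, and LOS yields five quantities: "Reaction time, movement velocity, endpoint excursion, maximum excursion and direction control parameters are calculated during these trunk movements". No combined LOS score is defined.

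None of these measures, and none of the visits, is called primary.

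**The concern.** Children were randomised to rehabilitation plus postural exercise or to rehabilitation alone. Whether the added exercise works is therefore a between-group question, and the Mann-Whitney tests answer it. The stated correction appears to protect a different set of tests, the changes from baseline inside each group. The between-group tests are left at 0.05 each, over an unstated number of measures and visits.

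Two things are at stake. First, 0.05 does not describe the risk of wrongly concluding that the groups differ somewhere. Second, a reader cannot tell which result was meant to decide the question. One p just under 0.05, on one measure at one visit, could be presented as showing that the exercise programme works when it is weak evidence.

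**Working it through.** **The plan's own figure.** 0.05/3 = 0.0167, which rounds to the stated 0.017. Three is the number of baseline-to-visit Wilcoxon comparisons (6 weeks, 3 months, 6 months). Position and arithmetic both point to those comparisons.

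**Number of between-group tests.** The document does not give this, so it is derived. I assume the CFQR total only, post-treatment visits only, and one test per measure per visit.

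- FEV1, VAS, CFQR total, MST and five LOS parameters: 9 measures × 3 visits = 27
- Cobb and Modified Cobb angles at six months: 2 × 1 = 2
- Total: 27 + 2 = 29
- If LOS counted as one outcome: 5 × 3 + 2 = 17
- If eight CFQR content areas replaced the total: 16 × 3 + 2 = 50

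**Chance of at least one false group difference.** I assume no true effect and two-sided tests. Under independence the formula is 1 − (1 − α)^k.

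- 29 tests at 0.05: 1 − 0.95^29 = 0.774
- 17 tests at 0.05: 1 − 0.95^17 = 0.582
- 29 tests at 0.017: 1 − 0.983^29 = 0.392
- 17 tests at 0.017: 1 − 0.983^17 = 0.253

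The measures come from the same children, so independence is only a reference. The documents give no correlations. The pairs below are assumptions, and the figures come from simulated multivariate normal test statistics. The first number in each pair is the correlation between visits for one outcome, the second the correlation between outcomes.

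| Correlation | 29 tests at 0.05 | 17 tests at 0.05 | 29 tests at 0.017 | 17 tests at 0.017 |
|---|---|---|---|---|
| independent | 77% | 58% | 39% | 25% |
| 0.7 / 0.3 | 59% | 44% | 28% | 19% |
| 0.9 / 0.5 | 42% | 31% | 19% | 13% |
| 0.9 / 0.7 | 30% | 24% | 13% | 10% |
| 0.9 / 0.9 | 17% | 15% | 7% | 6% |

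**Discreteness.** An exact Mann-Whitney test usually rejects less often than its nominal level. Without ties, the attained size at nominal 0.05 is 3.2% at 5 per group, 3.8% at 7 and 4.3% at 10. The independent 29-test figure then becomes 61%, 67% and 72%.

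**What Holm would require over 29 tests.** The smallest p is compared with 0.05/29 = 0.00172, the next with 0.05/28, and so on. Attained error is 4.9% under independence, and 3.9%, 2.7% and 2.0% at 0.7/0.3, 0.9/0.5 and 0.9/0.7.

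The smallest two-sided exact p with equal groups and no ties is 2/C(2n, n):

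- 5 per group: 2/252 = 0.0079
- 6 per group: 2/924 = 0.0022
- 7 per group: 2/3432 = 0.0006

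The first Holm limit is therefore out of reach below 7 per group. With the plain normal approximation (no tie or continuity correction), complete separation at 7 per group gives p = 0.001745, just above 0.001724, so the limit is missed there too.

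**The case against.** The strongest reply is that the size of the problem cannot be known. The 29 is a reviewer's count, the correlations are assumed, and independence is implausible for repeated measures and for five parameters from one balance test. That stands. A reader might infer that 29 is the full set of possible tests and that 77% is the most the error could be. The documents support neither. Testing CFQR content areas or baseline values would raise the count, while correlation and, usually, exact-test discreteness lower the error. What survives is that every assumed pattern at 0.05 gives well over 5%, including the extreme 0.9/0.9 case at 17%.

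A second reply is that the 0.017 sentence refers to the results in general and so covers the group comparisons too. The wording allows this. It narrows the gap without closing it, because dividing by three allows for visits but not for outcomes. Only near 0.9/0.9, where pain, lung function, balance and spinal angles would be almost interchangeable, does the error come close to 5% (7%).

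A third reply is that a primary outcome may be named elsewhere. A reader might infer that the trial had none. The documents show only that this one names none. The timing is also unclear, since the document is dated January 2017 but describes, in the past tense, a study run from March to October 2017. The fix therefore depends on whether a dated record exists.

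Last, Holm over 29 tests is not the only sound remedy when nothing was named in advance and the sample size is not given. That also stands, and exploratory reporting is offered as an equal alternative.

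**Conclusion.** The concern holds. As written, the randomised comparison is tested at 0.05 across an unstated number of measures and visits, with nothing to identify the deciding result. The one stated correction matches the within-group comparisons. Under the 29-test count, the chance of at least one false group difference is about 30% to 59% for the three middle correlation patterns, with 77% as the independence reference. If 0.017 also governed these tests, the range for the same patterns would be about 13% to 28%.

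Confidence is high that the document omits a rule. It is lower for the size, which rests on the assumed count, the assumed correlations, two-sided tests and no true effect on any outcome. This should be fixed; it does not make the data unusable.

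**What to change.** 1. State how many between-group tests were done, on which measures and at which visits.
2. If a dated record made before the data were seen names one primary outcome and visit, test that at 0.05. Treat the rest as secondary, with Holm applied to them only if the primary succeeds.
3. If there is no such record, choose one of two courses. Either apply Holm across all between-group tests performed (smallest p against 0.05/29 = 0.0017 if all 29 were done), or report all between-group results as exploratory, with estimates and confidence intervals, and make no confirmatory claim from an isolated p below 0.05.
4. Base the conclusion about the added exercise on between-group results. A change within one group, significant or not, is not evidence that the groups differ.

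**Cost.** No new data are needed. The statistical section is reworded, existing p-values are compared with the new limits or reported with intervals, and conclusions resting on an isolated result are rewritten. Isolated results below 0.05 no longer count as confirmed. Holm is conservative with correlated tests, with attained error of about 2% to 4% at the three middle patterns. Over 29 tests it cannot be met with fewer than 7 children per group using exact p-values without ties, or at 7 per group with the plain normal approximation. In those cases exploratory reporting is the course to take.

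### The within-group test scheme, with its three-comparison cut-off of 0.017, makes no exception for the Cobb and Modified Cobb angles, which have only one pre-post comparison each

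*Combined protocol and SAP*

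**What the plan says.** The opening study description sets two measurement schedules. For FEV1, pain, quality of life, shuttle test and limits of stability: "All tests were performed before treatment and six weeks, three months and six months after treatment". For the radiographs: "Cobb and Modifiye Cobb angles were measured on radiographic examinations to evaluate spinal deformities before and six months after treatment".

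The Statistical analysis section does not carry this distinction through. It names the tests in one sentence, which begins "The Mann-Whitney U test was used to compare the measurement values between the two groups, and the Friedman test was used to compare the intra-group", and then sets the general level: "A statistical significance level of $p < 0,05$ was accepted". The pairwise follow-up is "The Wilcoxon test was used to compare pre-treatment and post-treatment 6th-week, 3rd-month and 6th-month values separately", and the next sentence is "Bonferroni correction was considered $p < 0,017$ statistically significant for evaluating the results". The only analyses specific to the radiographs are the correlation between two clinicians' readings and the intraclass correlation. No within-group test or threshold is stated for the angles themselves.

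**The concern.** A Bonferroni divisor should equal the number of comparisons in the family. Three is right for an outcome with three post-treatment visits. An angle with one post-treatment film has one comparison, so there is nothing to correct across visits.

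The choice of test raises a second issue. A Friedman test on two time points ranks each child's two values as 1 and 2, so it uses only the direction of change. That makes it a sign test. It discards the size of the change, which the Wilcoxon signed-rank test uses.

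The angles are the trial's measures of spinal deformity, and the added treatment is a postural program. At stake is a within-group change in angle being reported as non-significant only because a four-visit scheme was applied to two-visit data. Even if the scheme was never meant for the angles, the plan gives no rule for choosing between 0.017 and 0.05 or between Friedman and Wilcoxon. A p-value of 0.03 for an angle would be significant under one choice and not under the other.

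**Working it through.** **Inputs.** From Statistical analysis: general level 0.05, corrected cut-off 0.017, three Wilcoxon comparisons. From the study description: four visits for the functional outcomes, two for the angles. Group size and effect size are not stated, so those used below are assumptions.

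**1. The plan's own figure.** Bonferroni threshold = α/m. With α = 0.05 and m = 3, 0.05/3 = 0.016667, which prints as 0.017. Other divisors do not fit: m = 2 gives 0.025 and m = 4 gives 0.0125. The cut-off therefore matches the three comparisons named in the sentence before it.

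**2. Comparisons per outcome and group.**

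| Outcome | Visits | Pre-post comparisons | α/m |
|---|---|---|---|
| FEV1, VAS, CFQR, MST, LOS | 4 | 4 − 1 = 3 | 0.0167 |
| Cobb, Modified Cobb (each) | 2 | 2 − 1 = 1 | 0.05 |

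If 0.017 is applied to an angle, the threshold is 0.05/0.017 = 2.94 times stricter than one comparison needs. If the two angles are taken as one family, the threshold is 0.05/2 = 0.025 and the ratio is 0.025/0.017 = 1.47.

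**3. Power cost, normal approximation.** The two-sided critical values are 1.960 at 0.05 and 2.387 at 0.017.
- 80% power at 0.05 implies a standardised shift of 1.960 + 0.842 = 2.802. At 0.017, power is Φ(2.802 − 2.387) = 66.1%.
- 90% power implies a shift of 1.960 + 1.282 = 3.242. At 0.017, power is Φ(3.242 − 2.387) = 80.4%.

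**4. Power cost, simulated.** Normally distributed changes, mean change 0.65 SD, one pre-post comparison. Ranges show the spread over repeated simulations.

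| Children per group (assumed) | Wilcoxon at 0.05 | Wilcoxon at 0.017 | Two-visit Friedman at 0.05 |
|---|---|---|---|
| 15 | 62–63% | 41–42% | 43–44% |
| 20 | 76–78% | 58–59% | 58–59% |
| 30 | 92–93% | 82–83% | 77–78% |

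The Friedman column can be checked directly. With n = 20, the statistic is (b − c)²/n, where b and c count increases and decreases. A 15 to 5 split gives 100/20 = 5.0, above the 3.84 cut-off; 14 to 6 gives 64/20 = 3.2, below it. The chance that a child changes in the true direction is Φ(0.65) = 0.742, and the probability of at least 15 such children out of 20 is 58.5%.

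**5. Holm against Bonferroni for the four-visit outcomes.** Holm compares the smallest p-value with 0.05/3, the next with 0.05/2 and the last with 0.05, stopping at the first failure. It holds the 5% family error and rejects whatever Bonferroni rejects. With 20 children, a 0.65 SD change at each visit and an assumed correlation of 0.5, average power per comparison was about 67% for Holm and 58% for Bonferroni.

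**The case against.** The strongest reply is that the plan never says 0.017 governs the angles. The cut-off follows directly on a sentence naming three comparisons, two of which the angles cannot have, and a general level of 0.05 stands nearby as the natural default for a single test. This is fair: the scope is implied by the lack of an exception and is not stated. It does not close the gap. The six-month film does yield a 6th-month value, Wilcoxon is the only pairwise pre-post test named, and 0.017 is the only cut-off attached to it. The Friedman sentence is equally unrestricted.

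Four stronger readings are tempting, and the documents do not support them.

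- **That 0.017 is an arithmetic error.** It is 0.05/3 to three decimals and correct for the four-visit outcomes. The rounding moves the family bound only from 0.050 to 3 × 0.017 = 0.051. For exact two-sided Wilcoxon tests without ties or zero differences, no attainable p-value falls between 0.016667 and 0.017 for any group size from 6 to 27.
- **That the plan knowingly applies a wrong threshold to the spinal outcomes.** It is silent on them.
- **That false positives are inflated.** Too strict a cut-off, or a less sensitive test, costs power.
- **That the randomised comparison is compromised.** The Mann-Whitney test between groups is separate from the pairwise correction, and the angles' between-group result does not depend on this point.

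It is also fair that no primary outcome is named, so the angles cannot be said to rank above the rest, and that the power figures depend on an assumed effect and group size. Holm in place of Bonferroni is an improvement, not the repair of an error.

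**Conclusion.** The point holds in a limited form. The within-group scheme was built for four visits, and nothing in it exempts two outcomes measured at only two. Followed literally, it gives each angle a correction for two comparisons that are never made and a Friedman test that is only a sign test. With an assumed 20 children per group and a 0.65 SD change, either feature alone lowers within-group power from about 76% to about 58%. Over 15 to 30 children at that effect, the loss from the cut-off is about 21 to 10 percentage points (62 − 41 = 21; 92 − 82 = 10).

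These losses arise only if the scheme is applied to the angles. If it is not, what remains is an unspecified test and threshold for two outcomes. On either reading the text should be completed, and the consequence stays within the within-group analyses.

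**What to change.** Make two changes to the Statistical analysis section.

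1. State that the three-comparison correction covers only the week-6, month-3 and month-6 Wilcoxon comparisons of the four-visit outcomes, within each outcome and group. Preferably replace Bonferroni with Holm's step-down; if Bonferroni is kept, write the threshold as 0.05/3.
2. State that each angle is tested once within group, six months against baseline, by Wilcoxon at 0.05, with no Friedman test. If the two angles are to be one family, use 0.025 for each.

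The cost is a few sentences and no new data. The angle tests become less strict: at 0.05 each, the error bound over the two angles is 2 × 0.05 = 0.10, against 2 × 0.025 = 0.05 for the family version, so the choice should be stated with its reason. The document describes the study as already performed. If the change is made after data have been seen, it should be labelled as a correction of the plan and the angle p-values reported exactly, so that readers can apply either threshold.

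### Do the correlation analysis, the unspecified ICC and the unstated choice of reading for the Cobb angles call for a change to the plan?

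*Combined protocol and SAP*

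**What the plan says.** The opening study description sets the radiographic outcomes and their timing: "Cobb and Modifiye Cobb angles were measured on radiographic examinations to evaluate spinal deformities before and six months after treatment". Under Radiographic evaluation, the document defines each angle by its landmarks. For the first it says "The Cobb angle was measured on antero-posterior scoliosis graphs by the angle between the superior end plate of the vertebra corpus where the curve begins"; for the second, "The Modified Cobb angle was found on lateral scoliosis graphs by the angle between the superior end plate of the T4 vertebra corpus". Neither definition mentions a reader, averaging or adjudication.

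The Statistical analysis section shows that there were two readers and gives two analyses of their readings. The first is "A Spearman and Pearson correlation analysis was performed to examine the relationship between the radiographic values measured by two different clinicians". The second is "The intraclass correlation coefficient for the interobserver reliability analysis was calculated for radiographic measurements". The ICC is given no model, no type (consistency or absolute agreement), no unit (single or average reading) and no confidence interval.

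For the outcome comparison, the same section says "The Mann-Whitney U test was used to compare the measurement values between the two groups", and it uses Wilcoxon tests for change within a group. It does not say which clinician's angle enters either test.

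**The concern.** Two things look wrong. First, correlation measures association, not agreement. If one clinician reads every film a fixed number of degrees higher, neither Pearson nor Spearman registers it. Naming an ICC does not settle the matter, because a consistency ICC ignores the same offset and an absolute-agreement ICC does not. A report could therefore claim high reliability for readers who differ systematically.

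Second, two sets of angles exist for at least some films, and no rule says which is analysed. That leaves at least three candidates for each angle: one reader, the other reader, or their mean. In principle the choice could be made after the results are seen. A single reading is also usually noisier than a mean of two, so some precision may be lost. The radiographic outcomes are the only ones exposed.

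**Working it through.** The documents give no ICC, reader error, between-child SD, sample size or expected angle change, so there is no stated figure to reproduce. Every numerical input below is an assumption, shown over a range.

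**1. How far can correlation and the ICC forms diverge?** Let Sb be the between-child SD, Se the reader error SD and b a constant offset between two readers.

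- Pearson = consistency ICC (single reading) = Sb² / (Sb² + Se²)
- Absolute-agreement ICC (single reading) = Sb² / (Sb² + Se² + b²/2)

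With b = 5 degrees, b²/2 = 12.5.

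| Sb | Se | Pearson and consistency ICC | Absolute-agreement ICC |
|---|---|---|---|
| 10 | 0 | 1.0 | 100/112.5 = 0.889 |
| 5 | 0 | 1.0 | 25/37.5 = 0.667 |
| 10 | 3 | 100/109 = 0.917 | 100/121.5 = 0.823 |
| 5 | 3 | 25/34 = 0.735 | 25/46.5 = 0.538 |

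The statistical point is correct: the offset leaves correlation and the consistency ICC untouched, and the ICC form can materially change the reported reliability.

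**2. Are the correlations offered as the agreement measure?** Set the two sentences side by side. The correlations are assigned to the relationship between the readers' values; the ICC is assigned to interobserver reliability. The correlations are supplementary, and they are not empty. For two readers the consistency ICC equals 2cov/(s1² + s2²). Since s1² + s2² is at least 2·s1·s2, it cannot exceed a positive Pearson coefficient. A low correlation therefore rules out good agreement, and a high one beside a clearly lower absolute-agreement ICC points to a systematic difference.

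**3. Does an offset reach the treatment comparison?** If one reader is used for every film, every angle shifts by the same amount. If the mean is used, every angle shifts by b/2. Adding a constant to all values leaves the ranks, and so the Mann-Whitney statistic, unchanged. In the pre/post Wilcoxon test the constant cancels within each child. Harm would need readers to be mixed across groups or time points, and nothing in the documents suggests that.

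**4. What would averaging gain?** Let R be single-reader reliability and c the correlation between the two readers' errors. The fall in variance of a six-month value is (1 − R)(1 − c)/2.

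| R | c = 0 | c = 0.5 |
|---|---|---|
| 0.80 | 0.20/2 = 10% | 5% |
| 0.90 | 0.10/2 = 5% | 2.5% |
| 0.98 | 0.02/2 = 1% | 0.5% |

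The largest entry is like 1/0.90 = 1.11, about 11% more children; R = 0.90 with c = 0 is like 1/0.95 = 1.05, about 5% more. Because the planned test is rank-based, these equivalents are approximate. They also require both clinicians to have read every film, which the document does not state.

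**The case for a change.** The strongest case for a change is that it would be cheap and would close a real freedom. One sentence could name the analysed reading, another could specify a two-way absolute-agreement ICC with a confidence interval, and limits of agreement would show readers what correlation hides. The gain from averaging is also larger for pre/post change. With reliability 0.8 and a true pre/post correlation of 0.9, and with single-reading variance set to 1, the variance of change falls from 2(0.8)(0.1) + 2(0.2) = 0.56 to 2(0.8)(0.1) + 0.2 = 0.36, which is 36%.

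Part of this stands. The ICC form and the analysed reading are absent, and a good report would give both. The rest is weaker:

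- The 36% concerns change within a group, which does not estimate the effect of the added exercise. The stated between-group test is on measurement values.
- The mean is one acceptable choice among several; a single reader used throughout also avoids bias from a constant offset.
- The cover date is January 2017, but the text describes the study and its analysis in the past tense. If the analysis had already been run, naming a reading now would itself be a choice made after the results, so the selective-choice worry would be met by disclosure and not by a revised plan.

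**Conclusion.** The observation is accurate, but no change to the plan follows. No stated rule produces a wrong result: reliability is already assigned to an ICC, and the correlations beside it do no harm. No bias in the randomised comparison is shown, provided the analysis uses the same reader, or the mean, for every film, as any sensible analyst would. The precision forgone by not averaging is about 1% to 10% of the variance of six-month values, or 0.5% to 5% if reader errors correlate 0.5. Those ranges rest on assumed reliabilities of 0.8 to 0.98 and on both clinicians having read every film. The ICC contrasts (1.0 against 0.89 or 0.67) rest on an assumed 5-degree offset with no random error. They affect how reader reliability is described, not the estimated treatment effect. The ICC type and the reading used belong in the report; leaving them out here is missing detail on an ancillary analysis and is not shown to alter any trial conclusion.
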